### 3.7 Statistical analysis.

Demographics between smokers and nonsmokers will be compared using  $t$  tests or Chi-Square tests, as appropriate. Scores on psychological tests such as depressive symptoms at baseline will be compared between groups and may be used as covariates in subsequent analyses. All outcomes will be summarized descriptively and assessed for normality prior to analysis using normal probability plots and Kolmogorov test statistics. Transformations or nonparametric analyses will be performed as necessary. All tests will be two-sided and considered statistically significant at  $\alpha = 0.05$ . Post-hoc comparisons will be conducted as necessary with significance levels adjusted for multiple comparisons basing the adjustment on the number of conceptually related statistical tests within each hypothesis. All statistical analyses will be conducted using SAS version 9.3 (Cary, NC).

**Aim 1. To determine if amphetamine-induced DA release is blunted during abstinence in tobacco smokers compared to nonsmokers.** Hypothesis 1. We hypothesize that amphetamine-induced striatal DA release will be blunted in smokers compared to nonsmokers. Power Calculations for Hypothesis 1: Our preliminary data revealed blunted amphetamine-induced DA release ( $d=0.91$ ) in the ventral striatum among smokers ( $-21\% \pm 12.0$ ) compared to nonsmokers ( $-29\% \pm 6.3$ ). Assuming a two-sided  $t$ -test with  $\alpha=0.05$ , 40 nonsmokers and 50 smokers assessed after 14-21 days of abstinence will provide 80% statistical power to detect effect sizes as small as  $d=0.63$ , which compares favorably with the effects observed above.

Regional [ $^{11}\text{C}$ ]PHNO uptake for each subject will be quantified as  $\text{BP}_{\text{ND}}$  described above for each ROI and will represent the primary outcome measure for the proposed experiments. Repeated measures ANOVA will be used to evaluate the change between scans ( $\Delta\text{BP}$ ) for brain measures for the scans.  $\Delta\text{BP}$  will be computed as  $[(\text{BP}_{\text{baseline}} - \text{BP}_{\text{condition}}) / \text{BP}_{\text{baseline}} \times 100]$ . Analysis will be conducted using SAS version 9.1 (Cary, NC).  $N=20$  subjects per group is necessary to detect differences between smokers and nonsmokers. Potential associations, e.g., relationship between magnitude of dopamine release and time to relapse, will be examined using correlation analysis with Type I error corrected for multiple comparisons. Exploratory analyses of the other cognitive and behavioral measures and their relationship to relapse will also be performed.

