**Aim 1. To determine amphetamine-induced DA release in nonsmokers and in tobacco smokers during acute and prolonged withdrawal.** We will scan 50 Healthy Smokers and 50

Non Smoker healthy controls. Each tobacco smoking subject will participate in up to 4 [C]PHNO PET scans, one pair of scans during the first 2 weeks of smoking abstinence and, for those who remain abstinent, the option to have another pair of scans at 2-8 weeks abstinence. We aim to have at least one week in between sets of scans. Ideally, two PET scans will be carried out in the same day. We first obtain a baseline scan, then approximately three hours before the second scan, amphetamine (0.5 mg/kg, PO) will be administered. Nonsmokers will only be asked to participate in one set of scans. We hypothesize that smokers at 1-2 weeks of withdrawal will have amphetamine-induced DA release that is blunted compared to healthy nonsmokers. We also hypothesize that the smokers who are scanned again at 2-8 weeks withdrawal will exhibit some ‘normalization’ of the dopamine system and will have a larger amphetamine-induced DA release compared to their first scan. We hypothesize that smokers with amphetamine-induced DA release similar to nonsmokers, or that increases over time, will have better abstinence outcomes.

2. **Background:** Describe the background information that led to the plan for this project. Provide references to support the expectation of obtaining useful scientific data.

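### The PHNO smoker-nonsmoker comparison uses repeated measures ANOVA, which pools variances although the pilot SDs are 12.0 and 6.3; an unequal-variance test on first scan sets should be named instead

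*Combined protocol and SAP*

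**What the plan says.** All references are to the PHNO (amphetamine) protocol unless stated otherwise.

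- **Analysis.** Section 3.7 (Statistical analysis) and section 11 (Statistical Considerations) both say: "Repeated measures ANOVA will be used to evaluate the change between scans". The change is defined as the percentage fall in binding potential from baseline to the post-amphetamine scan. No covariance structure, variance assumption or rule for a missing scan set is given. The only fallback is a normality check followed by a transformation or a nonparametric test.
- **Hypothesis 1.** Striatal dopamine release is expected to be blunted in smokers. The pilot changes are -21% (SD 12.0) in smokers and -29% (SD 6.3) in nonsmokers. The sample-size statement is that "40 nonsmokers and 50 smokers assessed after 14-21 days of abstinence will provide 80% statistical power" for a standardized difference of 0.63. The test is a two-sided t-test at 0.05.
- **Scan sets.** Under Aim 1 in Section II, smokers have a first pair of scans and, "for those who remain abstinent, the option to have another pair of scans at 2-8 weeks abstinence". For controls, "Nonsmokers will only be asked to participate in one set of scans".
- **Normalization.** Aim 1 also predicts that smokers who are scanned again will show larger release than at their first set. Section 3.7 names no separate analysis for this.

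**The concern.** A method that assumes a common variance is named for two groups whose SDs differ by a factor of 1.9 in the plan's own pilot data. Whether that helps or harms depends on which group is larger. If the more variable group is larger, the pooled test is conservative and loses power. If it is smaller, the test rejects too often. Smokers are the larger group at the first set and would probably be the smaller group in any second-set comparison, because the second set depends on staying abstinent.

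The text also leaves open how the second set enters the analysis. If scan set were made a within-subject factor in a classical ANOVA, a smoker without a second set could drop out of the Hypothesis 1 comparison as well. That comparison needs only the first set.

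**Working it through.** **1. The plan's own power figures.** By the noncentral t, 40 and 50 subjects at d = 0.63 give 83.6% power, and 80% power is reached at d = 0.60. The stated 80% reproduces with 40 per group (79.5%), so the statement is slightly cautious for 40/50. The separate figure of 20 per group reproduces at d = 0.91 (80.1%). None of these calculations allows for unequal variances.

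**2. Why the named method pools.** With two scans per subject, the group-by-scan F test equals the square of the pooled t statistic on the within-subject change. If one percentage change per subject is analysed, the group F test is again the pooled t squared.

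**3. Inputs.** SDs of 12.0 and 6.3 are from section 3.7. The ratio is 12.0/6.3 = 1.90, and the variance ratio is 144/39.69 = 3.63. The pilot gap is 29 - 21 = 8 points. I assume the pilot SDs hold in the trial and that changes are normal.

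**4. Standard error used against true standard error**, with n_S smokers and n_N nonsmokers:

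- pooled variance: s² = [(n_S - 1) × 144 + (n_N - 1) × 39.69] / (n_S + n_N - 2)
- SE used by the pooled test: √[s² (1/n_S + 1/n_N)]
- true SE: √(144/n_S + 39.69/n_N)

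For 50/40: s² = (49 × 144 + 39 × 39.69)/88 = 97.77. The SE used is √(97.77 × 0.045) = 2.098. The true SE is √(2.880 + 0.992) = 1.968. The pooled SE is too large by a factor of 1.066.

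| Smokers / nonsmokers | SE used / true SE | Type I error, pooled | Type I error, Welch |
|---|---|---|---|
| 50 / 40 (planned) | 1.066 | about 3.8% | 5.0% |
| 50 / 50 | 1.000 | 5.1% | 5.0% |
| 35 / 40 | 0.962 | about 6% | about 5% |
| 25 / 40 | 0.874 | 8.7% | 5.0% |
| 20 / 40 | 0.822 | about 10.7% | 5.0% |

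Error rates are simulated (60,000 replicates per row). The 50/50 row is included because Aim 1 gives 50 nonsmokers where sections 3.1, 3.7 and 5 give 40. The last three rows describe a hypothetical comparison of second-set smokers with all nonsmokers.

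**5. Power at 50/40.** For the 8-point pilot gap, pooled 97% and Welch 98%. For a 5-point gap (my illustration, not a figure from the plan), pooled about 66-67% and Welch 71%.

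**6. Normalization: does restricting to smokers scanned twice bias the change?** The PHNO protocol gives no retention, no test-retest correlation and no link between release and abstinence. Illustrative assumptions: SD 12, between-set correlation 0.6, 50% retention (the NCFHEB protocol, Aim 3, expects about that at 4-8 weeks), true change +4 points, and correlation r between measured first-set release and staying abstinent.

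| Abstinence depends on | r | Change in those scanned twice | Likelihood fit using all first sets |
|---|---|---|---|
| either | 0 | 4.0 | 4.0 |
| measured first-set release | 0.2 to 0.4 | 3.2 to 2.5 | 4.0 |
| underlying true release | 0.2 to 0.4 | 4.0 | 4.8 to 5.7 |

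The two mechanisms reverse which analysis is biased, and nothing in the documents says which applies.

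**The case against.** The strongest reply is that Hypothesis 1 is barely harmed. At the planned sizes the pooled test errs on the safe side, and power for the pilot gap is 97% against 98%. This stands. The case for change is that the mismatch is visible in the plan's own numbers, costs some power if the true gap is below the pilot gap, and is free to remove.

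Two stronger readings are tempting, and the documents support neither.

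- **Completers-only bias.** A reader might infer that smokers without a second set are deleted and that the estimates are therefore biased. No section makes scan set a factor or states a completers-only analysis. The natural reading of the repeated factor is baseline against post-amphetamine within one set, which every fully scanned subject has. Aim 1 frames normalization among smokers scanned again, so those smokers are the stated target. Aim 1 does hypothesize that release is related to abstinence, so selection is plausible, but step 6 shows that its effect on the change may be a shortfall or nothing. A mixed model is not a safe cure, because it can overstate the change in the direction of the plan's hypothesis.
- **Inflated false-positive rate.** A reader might take the 9-11% as applying to the main comparison. It belongs to a second-set comparison with nonsmokers that the plan does not state. A within-smoker change does not use the nonsmoker variance at all.

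**Conclusion.** The concern holds in a limited form. The named analysis pools variances that the plan's own pilot puts at a ratio of 3.63. At 50 smokers and 40 nonsmokers the result is a conservative test (about 3.8% instead of 5%) with a small loss of power: 4 to 5 percentage points at a 5-point gap and about 1 at 8 points. At 50/50 there is essentially no distortion. Anti-conservative error of about 9-11% would arise only if 20-25 second-set smokers were tested against 40 nonsmokers with a pooled variance.

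These figures rest on the pilot SDs holding and on approximate normality. The pilot group sizes are not stated, so the precision of the SD ratio cannot be judged. For normalization, the defect is that the analysis and its target group are not specified. The documents do not establish that the planned estimate is biased.

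**What to change.** In sections 3.7 and 11 of the PHNO protocol:

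1. Test Hypothesis 1 on every subject's first scan set with Welch's test, or with a model that has group-specific variances. State that a missing second set does not remove a smoker from this analysis. Name the set explicitly: the power statement refers to 14-21 days of abstinence, while Aim 1 places the first set within the first two weeks, and the two need reconciling.
2. Use the same unequal-variance approach for any contrast of second-set smokers with nonsmokers.
3. State that the normalization hypothesis concerns the within-smoker change among those scanned twice.
4. Report a mixed model using all first sets as a sensitivity analysis only. State its condition: it is unbiased if loss of the second set depends on observed first-set values, and it can overstate the change otherwise.

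The cost is a few sentences of text. No extra subjects or scans are needed, and the SAS software already named fits these analyses.

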- a) One MRI scan, which will take approximately 30-60 minutes. This will take place at the Anlyan Center at [name].
- b) Up to 8 weeks of smoking abstinence- meet with staff multiple times a week to ensure abstinence. For the first week the subject will meet with staff every day (barring an unforeseen circumstance that prevents the subject from meeting). Meetings will occur either at [name], the Yale PET center, or a meeting point midway between the subject and Yale due to distance. As the weeks proceed, meetings will taper down.
- c) Two sets of two PET scans with [C]PHNO approximately 1-2 weeks after quitting smoking and again at 2-8 weeks with at least a week break in between scan sets. Both scans of each set will take about 2 hours each and should be done on the same day. Starting up to 3 hours prior to the second [C]PHNO scan of the set, subjects will be asked to take a drug called amphetamine by mouth. These will take place at the Yale PET Center.

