#### Sequence of procedures

Order	Study procedure	How Long	When
1.	MRI scan/Day 0 appointment: This includes, mri, computer testing, cold pressor task, and withdrawal guidelines.	2 hours	After screening
2.	Smoking abstinence for about 2-8 weeks w/ daily appts for the first week tapering down as the weeks proceed..	2-8 weeks	After MRI scan
3.	Set of 2 PHNO PET scans with amphetamine challenge (with computer task and cold pressor task)	All Day	At ~1-2 weeks of smoking abstinence
4.	MRI scan(with possible computer task and Cold pressor task)	1 hour	At ~ 2-8 weeks of smoking abstinence
5.	Set of 2 PHNO PET scans with amphetamine challenge (with computer task and cold pressor task)	All Day	At ~2-8 weeks of smoking abstinence
6.	May be called followed up with Monthly to check in on smoking status	15 mins	monthly

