### **3.6 Image analysis.**

The primary outcome measure is the binding potential ( $BP_{ND}$ ), which in turn is proportional to the available receptor concentration ( $B_{avail}$ ), given that there is no change in affinity ( $K_D$ ) and that nondisplaceable (nonspecific and free) uptake does not differ between subjects and studies. We will examine the regions-of-interest listed below with the cerebellum used as a reference region because it is devoid of  $D_{2/3}$  receptors.

We obtain an MRI (as previously described) to use as a guide to place our regions of interest. This is because we can define anatomical regions of interest on the MRI, which provides structural information and then we can apply these regions of interest to the PET scans. The PET scans alone are not sufficient to identify brain regions. The PET image sets are aligned and resliced to yield images in the same planes and spatial system as the MRI images using AAL template. Primary ROIs will be caudate, putamen, ventral striatum, globus pallidus, and substantia nigra. Cerebellum will be the reference region.

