### 3.8 Contingency Reinforcement for Smoking Cessation (for healthy smokers)

We plan to image smokers during the first 8 weeks of abstinence. Contingency management techniques have been successfully used to help smokers quit smoking by a number of investigators including our group for many years (34-36).

We will help the subjects set a quit date and prior to the quit date they will meet with the research staff who will provide them with brief advice on quitting smoking based on AHCPR guidelines (The Smoking Cessation and Clinical Practice Guideline Panel and Staff, 1996). They will be advised about the risks and benefits of quitting smoking and told that they will be monitored daily to ensure abstinence. Subjects will be informed of payment schedules (see below) for CO levels indicating abstinence and also given information on how quit rates in the first week of smoking cessation predicted sustained abstinence. We use CO levels < 11 ppm to define abstinence from cigarettes. During the first week of abstinence we will obtain CO levels during contingency management meetings from subjects up to twice daily. In addition, we will obtain urine samples once daily to measure cotinine levels (a nicotine metabolite). These meeting will occur either in the research office, the Yale PET center, or in a midway point if subjects travel a far distance.

For each contingency management appointment, subjects will get \$10 if their CO levels are less than 1 ppm and urine cotinine levels are less than 100 ng/ml.

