**General inclusion criteria:**

- men and women, aged 18-55 years
- who are able to read and write
- who are able to give voluntary written informed consent
- have no current uncontrolled medical condition such as neurological, cardiovascular, endocrine, renal, liver, or thyroid pathology
- drink less than <21 drinks/week for women and less than <35 drinks per week for men
- If female, not pregnant or breast feeding
- If female of childbearing age, must use an acceptable method of birth control, as determined by the principal investigator
- do not suffer from claustrophobia or any MR contradictions
- willing to be followed up monthly after study participation via phone or email contact

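### Time to relapse is to be analysed by correlation, with no relapse event, follow-up end or rule for abstinent or lost smokers; Cox regression with a common horizon and two loss rules is a modest, cheap improvement.

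*Combined protocol and SAP*

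**What the plan says.** The point concerns the second protocol in the combined document, the [11C]PHNO amphetamine study.

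- **Method.** Section 3.7, repeated in section 11, says that the "relationship between magnitude of dopamine release and time to relapse, will be examined using correlation analysis", with Type I error corrected for multiple comparisons. No other method is named for this outcome. Section 3.7 also says "Transformations or nonparametric analyses will be performed as necessary".
- **Regions.** Section 3.6: "Primary ROIs will be caudate, putamen, ventral striatum, globus pallidus, and substantia nigra".
- **Follow-up.** Under section 3.1, smokers are monitored for up to 8 weeks and "meet with staff multiple times a week to ensure abstinence", daily in week 1 and then tapering. The Sequence of procedures table adds "May be called followed up with Monthly to check in on smoking status". The General inclusion criteria ask that subjects be "willing to be followed up monthly after study participation via phone or email contact". No end date is given.
- **Outcome.** Section 3.8 says "We use CO levels < 11 ppm to define abstinence from cigarettes". Its payment rule pays smokers "if their CO levels are less than 1 ppm and urine cotinine levels are less than 100 ng/ml". Relapse itself, and how to date it, are not defined.
- **Status of the question.** The Statement of Purpose puts relationships to relapse in the overall goal, Aim 1 hypothesises better abstinence outcomes with release like that of nonsmokers, and the Background says the study will determine whether release is associated with time to relapse.

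There is no power statement, expected relapse rate or loss rate for this analysis.

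**The concern.** Time to relapse is a censored outcome. For a smoker still abstinent at last contact, the plan has a lower bound on the relapse time and not the time itself. Before any correlation can be run, someone must decide which number that smoker contributes: the last contact time, a common ceiling, or nothing. As written, that decision would be made with the data in hand.

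The nonparametric option does not settle it. A rank correlation places abstainers correctly, as tied longest times, only if everyone is followed to the same end. None is set, and later contact is optional in the schedule. Smokers who go silent raise the same problem, more sharply, because those who relapse may be the ones who stop answering.

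At stake are the power and interpretability of the only analysis named for a question that the protocol lists among its goals. The result could also depend on an unrecorded choice.

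**Working it through.** **No stated figure to reproduce.** As a yardstick, suppose all 50 smokers had known relapse times. The correlation detectable with 80% power, two-sided 0.05, is tanh[(1.960 + 0.842)/√(50 − 3)] = tanh(0.409) = 0.39. At 0.05/5 = 0.01 (five primary regions) it is tanh[(2.576 + 0.842)/√47] = tanh(0.498) = 0.46.

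**Inputs from the documents.** Up to 50 smokers; two-sided alpha 0.05; five primary regions; monitored abstinence up to 8 weeks; first scan set at about 1-2 weeks.

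**Assumed inputs.** Hazard ratio (HR) 0.6 per SD of ΔBP (higher ΔBP is more release, so HR below 1 means later relapse). Exponential relapse times from the scan day. 50% abstinent at 8 weeks, borrowed from a closed aim (Aim 3) of the NCFHEB protocol. A scan about day 10 leaves 56 − 10 = 46 days, so the base hazard is about ln 2/46 = 0.015 per day, with about 50 × 0.5 = 25 relapses.

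**Power by simulation** (ranges cover Pearson and Spearman and repeat runs; *kept* means last contact is used as if it were the relapse time):

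| Follow-up | Cox | Correlation, kept | Correlation, abstainers dropped |
|---|---|---|---|
| Common 8-week end | 68-70% | 61-66% | 8-9% |
| Uneven, 14-120 days | 73% | 52-56% | 15-16% |

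Comparing methods within each run, the gain over *kept* is about 5-8 points with a common end and 17-21 points with uneven follow-up.

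**Sensitivity, Cox against correlation kept.**
- HR 0.7: 43% v 37-39% (common end), 45% v 30-32% (uneven).
- Common end, 30% abstinent: 81% v 74-77%. 70% abstinent: 47% v 41-44%.
- Alpha 0.01: 45% v 37-40% (common end), 49% v 28% (uneven).
- Complete follow-up to 365 days: Cox 90%, Pearson 88%, Spearman 80%.
- Different set-up (HR 1.6 per SD in the reverse direction, six months, 50% relapse): 63% v 56-57%; with 20% random loss, 60% v 42-43%.

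**Type I error.** With uneven follow-up unrelated to release, every method stays at 5-6%. If follow-up length correlates with release at 0.3 or 0.5 on the latent scale, *kept* correlation rises to about 10-14% or 22-30%; Cox stays at 5-6%.

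**Loss to contact** (46-day horizon, HR 0.6):

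| Who goes silent | Cox, lost censored | Cox, lost counted as relapsed | Correlation, kept |
|---|---|---|---|
| 35% of relapsers, regardless of release | power 53-54% | power 66-69% | power 62-64% |
| 50% of relapsers with below-average release, 20% of the others | power 25-27%, type I 10-11%, HR reads 0.70 | power 65-72%, type I 5-6% | power 59-68% (rank), type I 5% |
| 35% of relapsers and 20% of abstainers | power 51%, HR 0.59 | power 56%, HR 0.66 | not run |

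In the first row type I error is 5-6% for all three. Censoring is the weaker rule in the first two rows. In the third, counting lost smokers as relapsed pulls the HR towards 1. Neither rule is always right.

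**Precision.** SE(log HR) ≈ 1/√relapses. With 25 relapses: 0.6 × exp(±1.96/5) = 0.41 to 0.89. With 15: 0.6 × exp(±1.96/√15) = 0.36 to 1.00.

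**The case against.** The strongest case against is that the gain is small and the remedy has its own weakness. The 8-week monitored period is a natural common end, and with it Cox leads by only 5-8 points. The larger gap needs uneven follow-up of a length that no section states. The protocol offers this association only as an example among possible ones, without power. If relapsers fall silent, a Cox model that censors them can do worse than the correlation it replaces. All of that stands. It limits the claim and rules out censoring as the default.

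Several stronger readings are tempting but unsupported:

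- *The plan will discard abstinent smokers.* It does not say so. The 8-16% figures show what an open choice could cost; they do not describe the plan.
- *The correlation inflates false positives.* Only if follow-up length is related to release. Otherwise type I error stays near 5%.
- *The hypothesis about release that increases over time has no analysis at all.* The open-ended wording on associations can cover it, though without detail. It is a side matter here.
- *The two CO figures make relapse undefinable.* Abstinence is expressly defined in section 3.8; the other figure sits in the payment rule. They must be reconciled, but that does not prevent a definition.

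**Conclusion.** The concern holds in a limited form. The only method named for time to relapse cannot represent smokers still abstinent at last contact, and the relapse event, common end and loss rule that any method needs are missing. Cox regression is the better method at little cost. Its expected gain is about 5-8 power points with a common 8-week end and about 17-21 points with uneven follow-up.

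These sizes rest on assumed values for the HR, abstinence rate and follow-up pattern, since the documents give none for this cohort. The direction was the same across the HRs, abstinence rates and alpha levels tried. It reversed only when relapsers were lost and then censored.

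A reader might infer that the study's main result is at risk. It is not: the powered Hypothesis 1 comparison of smokers and nonsmokers does not use relapse data. This is a worthwhile correction to a secondary analysis.

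**What to change.** In sections 3.7 and 11, replace the correlation for this outcome with text to this effect:

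- **Model.** Time from the first PHNO scan day to relapse, by Cox regression on first-set ΔBP as a continuous covariate. Ventral striatum is the lead region; the other primary regions fall under the planned multiplicity correction. Report the HR per SD with 95% CI.
- **Horizon.** Smokers confirmed abstinent at a common horizon are censored there. The end of the 8-week monitored period (sections 3.1 and 3.8) is the natural choice and needs no added follow-up. For scans on days 7 to 14 it falls 56 − 14 = 42 to 56 − 7 = 49 days after the scan.
- **Event.** Define relapse and its date from the abstinence meetings, including whether a single lapse counts. Reconcile the two CO figures in section 3.8 before either is used.
- **Loss.** Report two rules side by side: lost smokers counted as relapsed at the first missed contact, and lost smokers censored at the last contact known abstinent. Censoring should be neither the sole nor the default rule.
- **If a correlation is kept.** Use a rank correlation with the common horizon and the same loss rules.

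The cost is a short SAP paragraph, one SAS procedure and two recorded dates per smoker (relapse, last known abstinent). Because monitoring is described as lasting up to 8 weeks, the text should say that status at the horizon is sought for every smoker. The estimate will still be imprecise, about 0.41-0.89 around an HR of 0.6 with 25 relapses, and should be reported as such.
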